8.2 SAFETY AND OTHER ASSESSMENTS

We will convene a Data Safety and Monitoring Board (DSMB) to review adverse events if any of the following occur:

- At the midpoint of enrollment
- If there is 1/3rd the expected enrollment at 6 months
- More than four serious adverse events at any time deemed definitely, probably, or potentially related to the intervention
- Rate of any serious adverse events is greater than 1% (including blood transfusion, hospitalization related to IUD, surgery related to IUD, death, IUD perforation, venous thromboembolism)

8.3 ADVERSE EVENTS AND SERIOUS ADVERSE EVENTS

8.3.1 DEFINITION OF ADVERSE EVENTS (AE)

The FDA definition of an Adverse event is any untoward medical occurrence associated with the use of an intervention in humans, whether or not considered intervention-related (21 CFR 312.32 (a)).

8.3.2 DEFINITION OF SERIOUS ADVERSE EVENTS (SAE)

An adverse event (AE) or suspected adverse reaction is considered "serious" if, in the view of either the investigator or sponsor, it results in any of the following outcomes: death, a life-threatening adverse event, inpatient hospitalization, a persistent or significant incapacity or substantial disruption of the ability to conduct normal life functions, or a congenital anomaly/birth defect. Important medical events that may not result in death, be life-threatening, or require hospitalization may be considered serious when, based upon appropriate medical judgment, they may jeopardize the participant and may require medical or surgical intervention to prevent one of the outcomes listed in this definition.

8.3.3 CLASSIFICATION OF AN ADVERSE EVENT

8.3.3.1 SEVERITY OF EVENT

For adverse events (AEs) not included in the protocol defined grading system, the following guidelines will be used to describe severity.

- **Mild** – Events require minimal or no treatment and do not interfere with the participant's daily activities.
- **Moderate** – Events result in a low level of inconvenience or concern with the therapeutic measures. Moderate events may cause some interference with functioning.

- **Severe** – Events interrupt a participant’s usual daily activity and may require systemic drug therapy or other treatment. Severe events are usually potentially life-threatening or incapacitating. Of note, the term “severe” does not necessarily equate to “serious”.

8.3.3.2 RELATIONSHIP TO STUDY INTERVENTION

All adverse events (AEs) must have their relationship to study intervention assessed by the clinician who examines and evaluates the participant based on temporal relationship and his/her clinical judgment. The degree of certainty about causality will be graded using the categories below. In a clinical trial, the study product must always be suspect.

- **Related** – The AE is known to occur with the study intervention, there is a reasonable possibility that the study intervention caused the AE, or there is a temporal relationship between the study intervention and event. Reasonable possibility means that there is evidence to suggest a causal relationship between the study intervention and the AE.
- **Not Related** – There is not a reasonable possibility that the administration of the study intervention caused the event, there is no temporal relationship between the study intervention and event onset, or an alternate etiology has been established.

OR

- **Definitely Related** – There is clear evidence to suggest a causal relationship, and other possible contributing factors can be ruled out. The clinical event, including an abnormal laboratory test result, occurs in a plausible time relationship to study intervention administration and cannot be explained by concurrent disease or other drugs or chemicals. The response to withdrawal of the study intervention (DE challenge) should be clinically plausible. The event must be pharmacologically or phenomenologically definitive, with use of a satisfactory rechallenge procedure if necessary.
- **Probably Related** – There is evidence to suggest a causal relationship, and the influence of other factors is unlikely. The clinical event, including an abnormal laboratory test result, occurs within a reasonable time after administration of the study intervention, is unlikely to be attributed to concurrent disease or other drugs or chemicals, and follows a clinically reasonable response on withdrawal (dechallenge). Rechallenge information is not required to fulfill this definition.
- **Potentially Related** – There is some evidence to suggest a causal relationship (e.g., the event occurred within a reasonable time after administration of the trial medication). However, other factors may have contributed to the event (e.g., the participant’s clinical condition, other concomitant events). Although an AE may rate only as “possibly related” soon after discovery, it can be flagged as requiring more information and later be upgraded to “probably related” or “definitely related”, as appropriate.
- **Unlikely to be related** – A clinical event, including an abnormal laboratory test result, whose temporal relationship to study intervention administration makes a causal relationship improbable (e.g., the event did not occur within a reasonable time after administration of the study intervention) and in which other drugs or chemicals or underlying disease provides plausible explanations (e.g., the participant’s clinical condition, other concomitant treatments).
- **Not Related** – The AE is completely independent of study intervention administration, and/or evidence exists that the event is definitely related to another etiology. There must be an alternative, definitive etiology documented by the clinician.

8.3.3.3 EXPECTEDNESS

The PI will be responsible for determining whether an adverse event (AE) is expected or unexpected. An AE will be considered unexpected if the nature, severity, or frequency of the event is not consistent with the risk information previously described for the study intervention.

8.3.4 TIME PERIOD AND FREQUENCY FOR EVENT ASSESSMENT AND FOLLOW-UP

The occurrence of an adverse event (AE) or serious adverse event (SAE) may come to the attention of study personnel during study visits and interviews of a study participant presenting for medical care, by communication from the participant to the study team, or upon review by a study monitor.

All AEs including local and systemic reactions not meeting the criteria for SAEs will be captured. Information to be collected includes event description, time of onset, clinician's assessment of severity, relationship to study product (assessed only by those with the training and authority to make a diagnosis), and time of resolution/stabilization of the event. All AEs occurring while on study must be documented appropriately regardless of relationship. All AEs will be followed to adequate resolution.

Any medical condition that is present at the time that the participant is screened will be considered as baseline and not reported as an AE. However, if the study participant's condition deteriorates at any time during the study, it will be recorded as an AE. Changes in the severity of an AE will be documented to allow an assessment of the duration of the event at each level of severity to be performed. AEs characterized as intermittent require documentation of onset and duration of each episode.

At each study visit, the investigator will inquire about the occurrence of AE/SAEs since the last visit. Events will be followed for outcome information until resolution or stabilization.

8.3.5 ADVERSE EVENT REPORTING

All adverse events will be reported to all three IRBs in a timely fashion (UCSD, UNM, UIC, and NMCSD) regardless of where the adverse event occurred. The on-site PI at each site will be responsible for monitoring adverse events and report any adverse events to each PI who will, in turn, report to their associated IRB. The management of information that is relevant to the protection of participants including adverse events, UPRs, protocol violations/deviations, interim results and protocol modifications will be the responsibility of each local PI at each site ([name] UCSD, [name] - UNM, [name] – NMCSD, [name] – UIC).

8.3.6 SERIOUS ADVERSE EVENT REPORTING

All serious adverse events will be reported to all three IRBs in a timely fashion (UCSD, UNM UIC, and NMCSD) regardless of where the adverse event occurred. The on-site PI at each site will be responsible for monitoring adverse events and report any adverse events to each PI who will, in turn, report to their associated IRB.

8.3.7 REPORTING EVENTS TO PARTICIPANTS

The IRB at each site will provide guidance to PIs on informing participants regarding AEs and SAEs as needed.

8.4 UNANTICIPATED PROBLEMS

8.4.1 DEFINITION OF UNANTICIPATED PROBLEMS (UP)

Unanticipated problems involving risks to participants or others to include, in general, any incident, experience, or outcome that meets all of the following criteria:

- Unexpected in terms of nature, severity, or frequency given (a) the research procedures that are described in the protocol-related documents, such as the Institutional Review Board (IRB)-approved research protocol and informed consent document; and (b) the characteristics of the participant population being studied;
- Related or possibly related to participation in the research (“possibly related” means there is a reasonable possibility that the incident, experience, or outcome may have been caused by the procedures involved in the research); and
- Suggests that the research places participants or others at a greater risk of harm (including physical, psychological, economic, or social harm) than was previously known or recognized.

8.4.2 UNANTICIPATED PROBLEM REPORTING

The investigators will report unanticipated problems (UPs) to the reviewing Institutional Review Board (IRB) and to the lead principal investigator (PI). The UP report will include the following information:

- Protocol identifying information: protocol title and number, PI’s name, and the IRB project number;
- A detailed description of the event, incident, experience, or outcome;
- An explanation of the basis for determining that the event, incident, experience, or outcome represents an UP;
- A description of any changes to the protocol or other corrective actions that have been taken or are proposed in response to the UP.

To satisfy the requirement for prompt reporting, UPs will be reported to the IRB within reasonable timing of the investigator becoming aware of the problem.

8.4.3 REPORTING UNANTICIPATED PROBLEMS TO PARTICIPANTS

The IRB at each site will provide guidance to PIs on informing participants regarding UPs as needed.

9 STATISTICAL CONSIDERATIONS

9.1 STATISTICAL HYPOTHESES

- Primary Efficacy Endpoint: Complete expulsion of IUDs placed in the early postpartum is non-inferior to IUDs placed at the standard interval time, assuming a 6% non-inferiority margin.
- Secondary Efficacy Endpoints:
 - The proportion of participants utilizing the IUD at 6 months postpartum will be greater in the EPP group compared to the interval group.
 - Partial expulsion of IUDs placed in the early postpartum is non-inferior to IUDs placed at the standard interval time, assuming a 6% non-inferiority margin.
 - There will not be a clinically or statistically significant difference in the proportion of participants diagnosed with a pelvic infection.
 - Proportion of participants agreeing or strongly agreeing that they are satisfied with the IUD, and the timing of IUD placement, will be similar between groups.

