9.2 SAMPLE SIZE DETERMINATION

We hypothesize that EPP IUD expulsion will be non-inferior to interval insertion. We propose that greater than or equal to a 6% difference in expulsion at 6 months postpartum between the two arms is clinically meaningful (6% non-inferiority margin). Therefore, we estimate that 404 women will be needed [202 in each arm] to achieve an 80% power to detect a difference of 6% in expulsion at 6 months at a significance level of .05 (two-sided alpha), assuming a 15% loss to follow up and that 5% of IUDs would not be placed after randomization (due to patient preference or new medical contraindication or inability to place the IUDs) and assuming a 4% expulsion rate in the interval group. We estimate that enrolling 404 patients allows us to achieve an 80% power to detect a difference of 6% or more between groups with a 1-sided type 1 error of 0.25%.

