9.4.3 ANALYSIS OF THE SECONDARY ENDPOINT(S)

Partial IUD expulsion and perforation will be analyzed with the same methods as the primary outcome. IUD discontinuation over the six-month study period will also be analyzed using survival analysis. Data will be censored either (1) at the last date of contact if a participant is lost to follow up or (2) time of IUD removal. The Log-rank test will be used for an unadjusted comparison of the two survival functions. This will be presented graphically using Kaplan-Meier curves.

For other secondary outcomes, normally distributed, continuous variables will be compared using Student's t-tests as appropriate. The Mann-Whitney U test will be used to compare other continuous variables that are not normally distributed. Proportions will be compared using chi-square tests. For small cell sizes, Fisher's exact test will be used as appropriate.

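### Pelvic infection and satisfaction are hypothesised to be alike in the two arms, but are assigned only tests for a difference, with no margin or confidence-interval criterion

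*Combined protocol and SAP*

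**What the plan says.** Section 9.1 lists two secondary hypotheses of sameness. For infection: "There will not be a clinically or statistically significant difference in the proportion of participants diagnosed with a pelvic infection". For satisfaction: "Proportion of participants agreeing or strongly agreeing that they are satisfied with the IUD, and the timing of IUD placement, will be similar between groups". Neither comes with an expected rate, a margin, or a value for what would count as clinically significant.

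Section 9.4.3 divides the secondary outcomes. One group inherits the non-inferiority method: "Partial IUD expulsion and perforation will be analyzed with the same methods as the primary outcome". That method, in section 9.4.2, compares the confidence interval for the risk difference with the 6% margin. All other binary secondary outcomes, which include infection and satisfaction, fall under a general rule: "Proportions will be compared using chi-square tests. For small cell sizes, Fisher's exact test will be used as appropriate".

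The synopsis names pelvic infection and user satisfaction among the secondary objectives. The objectives table in section 3 lists neither. Section 9.2 computes power for expulsion only.

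**The concern.** A chi-square or Fisher test takes equality as its null hypothesis and looks for evidence against it. Failing to reject means only that the data did not contradict equality, and imprecise data seldom contradict anything. When the hypothesis of interest is itself sameness, this reverses the burden of proof: fewer participants, more loss to follow-up or rarer events all make the hoped-for result more likely.

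The trial uses the right logic elsewhere. For complete and partial expulsion it fixes a margin and asks whether the interval excludes it. That logic is dropped for infection in the same list of hypotheses.

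Infection is a plausible harm of earlier insertion, and section 2.2 says the trial is meant to support counselling on benefits and risks. An unsupported statement that infection does not differ could enter that counselling.

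**Working it through.** **Plan's own figure.** Section 9.2 says "404 women will be needed [202 in each arm] to achieve an 80% power to detect a difference of 6% in expulsion at 6 months". With 4% expulsion in both arms, a 6-point margin, two-sided alpha 0.05 and 80% power:

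n = (1.96 + 0.8416)² × 2 × 0.04 × 0.96 / 0.06² = 167.4, so 168 per arm.

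168 × 1.20 = 201.6, so 202 per arm and 404 in total. The stated size reproduces with that inflation, and it is a calculation for expulsion alone.

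**Evaluable number.** Section 9.2 assumes 15% loss to follow-up and 5% non-placement. 202 × 0.80 = 161.6, or 202 × 0.85 × 0.95 = 163.1. I use 162 per arm, with 202 (no losses) as the upper bound.

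**Assumptions.** The documents give no infection or satisfaction rates, so every rate below is an assumption, shown as a range. Section 9.4.3 states no significance level for these tests; I take two-sided 0.05. Section 9.4.3 sets no threshold for a small cell, so both tests are shown for infection.

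**Power by exact enumeration.** For x and y events in arms of size n:

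power = Σx Σy Bin(x; n, p1) × Bin(y; n, p2) × 1[test rejects at (x, y)]

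The chi-square test (uncorrected) rejects when (x/n − y/n)² / [2p̄(1 − p̄)/n] > 3.84, where p̄ = (x + y)/(2n). Fisher's test rejects when its two-sided p ≤ 0.05.

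| Assumed true rates | 162 per arm: chi-square / Fisher | 202 per arm: chi-square / Fisher |
|---|---|---|
| Infection 1% v 2% | 0.099 / 0.027 | 0.116 / 0.045 |
| Infection 1% v 3% | 0.229 / 0.115 | 0.281 / 0.172 |
| Infection 2% v 6% | 0.457 / 0.337 | 0.553 / 0.445 |
| Infection 3% v 9% | 0.636 / 0.547 | 0.734 / 0.669 |
| Satisfaction 90% v 85% (chi-square) | 0.276 | 0.327 |
| Satisfaction 90% v 80% (chi-square) | 0.720 | 0.811 |

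At 162 per arm, a threefold infection rate is therefore non-significant in:
- 77% (chi-square) or 88% (Fisher) of trials from a 1% base;
- 54% or 66% from a 2% base;
- 36% or 45% from a 3% base.

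**Precision that the trial can offer.** The approximate 95% half-width is 1.96 × √(2p(1 − p)/162):
- infection 2%: 1.96 × √(2 × 0.02 × 0.98/162) = 0.030, or 3 points;
- satisfaction 90%: 1.96 × √(2 × 0.90 × 0.10/162) = 0.065, or 6.5 points.

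**The case against.** **The decision rule is not written down.** Section 9.1 states expectations and section 9.4.3 says only how proportions will be compared. A reader might infer that the plan commits to declaring similarity whenever p>0.05. It does not say so, and the infection hypothesis also has a clinical limb. This stands. But the clinical limb has no value, the hypothesis itself refers to statistical significance, and no other basis for judging either hypothesis is offered.

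**The power figures are not properties of this trial.** A reader might take a single low range as the power for the differences that matter. The documents name no such difference and no base rate. Depending on the assumption, power runs from about 3% (Fisher, infection 1% v 2%) to above 70% (satisfaction 90% v 80%). This stands, and the figures are illustrations only.

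**A tripled infection rate would not be missed in general.** From a 3% base, a tripling is detected more often than missed under either test. Even at 2% v 6%, chi-square power passes one half if nobody is lost (0.553 at 202 per arm). The statement holds only if infection is rare.

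**Other safety monitoring exists.** Section 8.3.4 captures all adverse events, section 9.4.4 tabulates serious ones, and IUD-related hospitalisation counts towards a DSMB trigger in section 8.2. An increase would not simply go unseen. These provisions do not, however, supply a basis for a similarity claim, and no table of non-serious infections is promised.

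**Chi-square and Fisher are valid tests.** True, for a difference. The fault lies in pairing them with hypotheses of sameness.

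**Conclusion.** The concern holds as a mismatch between two secondary hypotheses and their analysis. Sections 9.1 and 9.4.3 together leave a non-significant difference test as the only prespecified evidence on infection and satisfaction, and that cannot establish similarity at any power. This follows from the text and needs no assumed rate.

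Its practical size does rest on assumptions: two-sided 0.05, about 162 evaluable per arm, and base rates the documents do not give. With infection at about 1-2%, a tripling would more often than not be non-significant; at 3% or above it would not. For satisfaction, a 5-point fall from 90% would usually go unflagged, and a 10-point fall usually would not.

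This should be corrected, but it concerns secondary outcomes and leaves the primary non-inferiority conclusion untouched.

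**What to change.** 1. In section 9.4.3, report pelvic infection and satisfaction as risk differences with two-sided 95% confidence intervals, using a method suited to rare events. Score intervals are one suitable choice.
2. In section 9.1, reword the two hypotheses as estimation of the difference between arms.
3. State that p>0.05 will not be interpreted as similarity.
4. If a similarity claim is wanted, the investigators should fix and justify a margin, and claim similarity only if the interval lies within it. The trial is not blinded (sections 4.1 and 6.2), so the margin should be set before any outcome data by arm are seen; fixing it only before database lock would be too late.

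**Cost.** Wording in two sections, with no new data or participants. Some statements of no difference will become inconclusive, given half-widths of about 3 points at 2% infection and 6.5 points at 90% satisfaction. Where a margin is used, one-sided non-inferiority power is approximately Φ(m/SE − 1.96), with SE = √(2p(1 − p)/162). At 2% infection in both arms, SE = 0.01556, so illustrative margins of 2 and 3 points give 25% and 49%. Those margins show the cost and are not recommendations. If no margin can be justified, items 1 to 3 are enough.

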9.2 SAMPLE SIZE DETERMINATION

We hypothesize that EPP IUD expulsion will be non-inferior to interval insertion. We propose that greater than or equal to a 6% difference in expulsion at 6 months postpartum between the two arms is clinically meaningful (6% non-inferiority margin). Therefore, we estimate that 404 women will be needed [202 in each arm] to achieve an 80% power to detect a difference of 6% in expulsion at 6 months at a significance level of .05 (two-sided alpha), assuming a 15% loss to follow up and that 5% of IUDs would not be placed after randomization (due to patient preference or new medical contraindication or inability to place the IUDs) and assuming a 4% expulsion rate in the interval group. We estimate that enrolling 404 patients allows us to achieve an 80% power to detect a difference of 6% or more between groups with a 1-sided type 1 error of 0.25%.

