5 STUDY POPULATION

Postpartum women delivering a baby at one of the 4 study sites are eligible: University of California, San Diego (UCSD); University of New Mexico (UNM); University of Illinois, Chicago (UIC), and the Naval Medical Center, San Diego (NMCS). 404 women will be enrolled between the 4 different study sites. Participants will be screened for eligibility according to the below criteria using a screening checklist. If eligible and interested in participating, a consent form will be signed.

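### Section 9.2: 404 women give about 79% power rather than the stated 80%, apparently because the 20% allowance was added as a mark-up instead of divided out (minor)

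*Combined protocol and SAP*

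**What the plan says.** Section 9.2 (Sample Size Determination) of the combined protocol and SAP states: "we estimate that 404 women will be needed [202 in each arm] to achieve an 80% power". The inputs given there are a "6% non-inferiority margin", 4% expulsion in the interval arm, and a test "at a significance level of .05 (two-sided alpha"). The allowance for losses is described as "assuming a 15% loss to follow up and that 5% of IUDs would not be placed after randomization". Section 5 (Study Population) repeats the target: "404 women will be enrolled between the 4 different study sites".

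The closing sentence of section 9.2 claims 80% power for the same 404 women "with a 1-sided type 1 error of 0.25" per cent, which is not the one-sided equivalent of two-sided .05.

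Section 9.2 does not give the evaluable number per arm, the expulsion rate assumed for the early arm, or the formula that turns an evaluable number into an enrolment target. Section 9.4.2 runs the primary comparison as a Wald test in the modified intention-to-treat (MITT) set. Section 9.3 limits that set to women who received an IUD within 6 months of delivery and have a known 6-month outcome.

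**The concern.** Both allowances in section 9.2 remove women from the primary analysis set: those never given an IUD and those without an outcome are outside the MITT set. If a fraction d of randomised women will be lost, the evaluable number must be divided by (1 − d) to get the enrolment target. Multiplying it by (1 + d) gives a smaller number that does not restore the required sample after losses. The printed 202 per arm is what the multiplication produces.

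At stake is the agreement between the two main planning figures, 404 women and 80% power. Section 9.2 is the only justification for the enrolment target, and a reader cannot check it as written because the intermediate steps are not shown.

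**Working it through.** **Inputs from section 9.2:** margin 0.06; interval rate 0.04; two-sided .05, so one-sided 2.5% (z = 1.95996); 80% power (z = 0.84162); losses of 15% and 5%; 202 per arm.
**Assumption made here:** the early-arm rate is also 0.04, the usual non-inferiority alternative.

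**1. Evaluable number per arm** (unpooled risk difference, in line with the Wald test in section 9.4.2):

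n = (1.95996 + 0.84162)² × 2 × 0.04 × 0.96 / 0.06² = 167.4, rounded up to 168.

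**2. Reproducing the plan's figure.** 168 × (1 + 0.15 + 0.05) = 168 × 1.20 = 201.6, rounded up to 202 per arm and 404 in total. This is an exact match. A compounded mark-up, 167.4 × 1.15 × 1.05 = 202.2, also lands close to 202.

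**3. Target with the losses divided out.**

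| Losses | Retained | Per arm | Total | Excess over 404 |
|---|---|---|---|---|
| Additive | 0.80 | 168/0.80 = 210 | 420 | 16 |
| Compounded, from 168 | 0.85 × 0.95 = 0.8075 | 168/0.8075 = 208.05, so 209 | 418 | 14 |
| Compounded, from unrounded 167.4 | 0.8075 | 167.4/0.8075 = 207.4, so 208 | 416 | 12 |

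**4. Power with 404 randomised.** Power = Φ(0.06/√(0.0768/n) − 1.96), where 0.0768 = 2 × 0.04 × 0.96.

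| Losses | Evaluable per arm | Power |
|---|---|---|
| Additive | 202 × 0.80 = 161.6 | 78.6% |
| Compounded | 202 × 0.8075 = 163.1 | 79.0% |
| Full overlap (the 5% lies within the 15%) | 202 × 0.85 = 171.7 | 81.0% |

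**5. Exact check.** Enumerating the two binomial distributions under the planned rule (upper Wald 95% limit below 6 points) gives 79.2%, 79.1% and 78.9% at 161, 162 and 163 per arm. Exact power is not monotone in n: it is 80.1% at 166 and 79.7% at 168. The figure of 168 for 80% therefore belongs to the normal approximation.

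**6. Sensitivity to the rates.** With an early-arm rate of 3.9% against 4%, power at 161.6 to 163.1 per arm is 80.4% to 80.7%. At about 162 per arm it is about 89% with both arms at 3%, about 70% with both at 5% (section 4.1 cites 3 to 5% for interval placement), and about 58% with the early arm at 5% against 4%.

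**7. The other printed error rate.** At one-sided 0.25%, 285 evaluable women per arm would be needed, and 404 randomised give about 48% power.

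**The case against.** The strongest reply is that the shortfall is negligible and depends on inputs the plan does not fix. Most of this stands.

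- **Size.** A gap of 1.0 to 1.4 points by normal approximation, or 0.8 to 1.1 points by exact enumeration at 161 to 163 per arm, is small beside the approximations in any such calculation. A reader might infer that the trial is materially underpowered or must recruit more women; the documents do not support either.
- **Early-arm rate.** Equality at 4% is not stated. Section 2.3.1 expects an early-arm risk no higher than standard care, and section 2.2 reports no complete expulsions in three early-placement studies. A rate only 0.1 point lower restores 80%. A higher rate would lower power, so this cuts both ways.
- **Overlap of losses.** It is tempting to say that power falls short however the losses are read. That is not so: section 9.2 does not say that the 15% and the 5% are separate groups, and full overlap gives about 81%. This is the favourable extreme, but it cannot be excluded from the text.
- **Cause.** Section 9.2 shows no inflation step, so the mark-up is an inference. One other route to 202 was found: a score-type (Farrington–Manning) formula at one-sided 5% needs 161.0 per arm, and 161.0/0.80 = 201.3. That error rate appears nowhere in section 9.2, but the section contradicts itself on the error rate, so the level actually used is unconfirmed.

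What the reply does not remove is the mismatch on the conventional reading. With equal rates, the stated two-sided .05 and losses that do not overlap, 404 and 80% do not agree, whichever route led to 404.

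**Conclusion.** The point holds as a minor one. Taking 4% in both arms, one-sided 2.5%, and losses of 15% and 5% that do not overlap, 404 randomised leave about 162 to 163 evaluable women per arm and about 79% power. The enrolment that would match 80% by the normal approximation is 416 to 420, so the difference is 12 to 16 women. The mark-up by 1.20 is the simplest explanation and reproduces 404 exactly, but it remains an inference.

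The gap does not threaten the trial's conclusion, and power depends far more on the true expulsion rates than on the inflation step. The conflict over the error rate in the same section is much larger in size and is a separate matter. Correcting it to one-sided 2.5% would still leave the stated power about 1 point too high under the assumptions above.

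**What to change.** Keep 404 and restate section 9.2, for example:

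*Assuming 4% complete expulsion in both arms and non-overlapping losses of 15% and 5%, 404 randomised are expected to leave about 162–163 evaluable women per arm in the MITT set, giving about 79% power at one-sided 2.5% (normal approximation; about 168 evaluable per arm would give 80%).*

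Show the inflation as division by (1 − loss), and say whether the two losses are taken as separate groups. Make the edit together with reconciling the one-sided 0.25% statement with two-sided .05, since the new sentence has to name a single error rate.

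The cost is a short rewrite of section 9.2 and a stated power about 1 point lower. No additional women are needed, and the analysis and decision rule are unchanged.
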